1. SYNOPSIS

TITLE	Treatment of multiple gingival recession defects with a coronally advanced flap or a modified tunnel technique and a volume stable three-dimensional xenogenic collagen matrix: a monocentric randomized clinical trial.
TRIAL LOCATION	PI: [name] [name] Dipartimento di Odontoiatria – Ospedale San Raffaele Direttore: [name] [name]
STUDY OBJECTIVES	To compare the outcomes of two muco-gingival surgery techniques, the modified coronally advanced flap (MCAF) for multiple recession defects (Zucchelli & [name] 2000) and the modified coronally advanced tunnel technique (MCAT) (Aroca 2013), performed in the Department of Periodontology of San Raffaele Hospital with the results reported in the literature. Secondarily, the study will evaluate whether patients report a preference in terms of discomfort and perception of aesthetics between the two surgical techniques.
STUDY DESIGN	Single center, National study, Comparative, Randomized, Open label
STUDY POPULATION	Main selection criteria: patients requiring root coverage procedures from the Dental Clinic of San Raffaele Vita-Salute University will be enrolled in the study. Inclusion criteria: multiple (i.e., at least 2) Miller Class I and/or II gingival recessions located in the maxillae, good general health, healthy periodontal conditions (FMPS and FMBS <25%). Exclusion criteria: smoking >10 cigarettes/day, nursing and pregnant female, contraindication against oral surgical interventions and against use of Fibro-Gide Total expected number of patients: 36 (18 for each group)
STUDY PROCEDURES	Recessions will be randomly treated by means of MCAF + CM or MCAT technique + CM. The following measurements will be recorded at baseline (prior to surgery), at 90, 180 and 360 days: Gingival recession depth (REC in mm), Keratinized tissue width (KTW in mm), Gingival thickness (GT in mm), Pocket probing depth (PPD in mm), BoP (Bleeding on Probing, PI (Plaque Index).
STUDY DEVICE	Fibro-Gide

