2. FLOW-CHART

Evaluation	Screening phase	Study phase						End of study
	Screening	Surgery	Post treatment follow-up					
		Day 0	Day 7±2	Day 14±4	Day 30±7	Day 90±15	Day 180±30	Day 360±60
Demographic data	X							
Inclusion/Exclusion criteria	X							
Previous medical history	X							
Informed consent	X							
Clinical examination	X							
PPD, BoP, PI	X					X	X	X
REC, KTW, GT	X					X	X	X
Oral hygiene instructions	X	X		X				
Treatment								
Randomization		X						
Mucogingival surgery		X						
Use of Fibro-Gide		X						
Compliance			X	X	X	X	X	X
Suture removal				X				
Photography		X	X	X	X	X	X	X
Pain assessment (VAS)			X					

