4.2. Secondary outcomes

- percentage of root coverage (RC %) at 3, 6 and 12 months
- keratinized tissue width (KTW) at 3, 6 and 12 months
- gingival thickness (GT) at 3, 6 and 12 months
- post-surgical pain (PP),
- amount of drug intake after surgery
- patient perception of aesthetics at 6 and 12 months
- color match (blending), contour (correct outline of the gingival margin at adjacent teeth), contiguity (evaluated based on the visible confluence between the treated area and the adjacent soft tissues), degree of keloid formation scored at the 1-year post-surgical evaluation will be measured by an expert periodontist.
- duration of surgery (from anesthesia to last suture).

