7.5. Follow-up

Patients will be followed for 12 months after surgery.

At 7 ± 2 days post-surgery – general examination, photographic picture of the treated site questionnaire about post-operative pain.

At 14 ± 4 days post-surgery – suture removal, photographic pictures of the treated site

At 1 month ± 7 days post-surgery – general examination, photographic picture of the treated site

At 3 months ± 15 days post-surgery - general examination, photographic picture of the treated site, measurements of the following parameters: Gingival recession depth (REC in mm), Keratinized tissue width (KTW in mm), Gingival thickness (GT in mm), Pocket probing depth (PPD in mm), BoP, PI.

At 6 ± 1 months post-surgery - general examination, photographic picture of the treated site, evaluation of the aesthetic outcome, measurements of the following parameters: Gingival recession depth (REC in mm), Keratinized tissue width (KTW in mm), Gingival thickness (GT in mm), Pocket probing depth (PPD in mm), BoP, PI.

At 12 ± 2 months post-surgery - general examination, photographic picture of the treated site, evaluation of the aesthetic outcome, measurements of the following parameters: Gingival recession depth (REC in mm), Keratinized tissue width (KTW in mm), Gingival thickness (GT in mm), Pocket probing depth (PPD in mm), BoP, PI.

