8.3. Statistical Methods

Statistical analysis will be performed using commercially available software (STATA) or R environment (www.r-project.org). Both patient- and tooth-level analysis will be performed for each parameter. Therefore, mean values and standard deviations (SD), as well other descriptive statistics, for the clinical variables will be calculated for each patient per treatment.

A mixed model will be built to take into account the variability due to patient and tooth factors differentially.

Accordingly, the significance of the difference within each group and between groups before and after treatment will be evaluated with the paired samples t-test or two independent samples t-test, as appropriated, regarding all numerical data (REC, KTW, GT, PPD, percentage of root coverage and VAS scale).

Fisher's exact test will be applied for categorical data (frequency of complete root coverage).

P-values will be computed by means of permutation methods to avoid any distributional assumptions or asymptotical approximation. Differences will be considered statistically significant when the p-value was <0.05 .

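### Patient-rated aesthetics, part of the secondary objective, has no pre-surgery reading; one added question would allow a baseline-adjusted comparison between arms

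*Combined protocol and SAP*

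**What the plan says.** Section 4 sets a secondary aim of comparing the two techniques on patient-reported discomfort and perceived aesthetics. Section 4.2 lists "patient perception of aesthetics at 6 and 12 months". Section 7.5 places an "evaluation of the aesthetic outcome" at the 6- and 12-month visits and at no other. The flow-chart in section 2 has no aesthetics row, and no instrument or scale is named anywhere.

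The synopsis introduces the baseline list with "The following measurements will be recorded at baseline (prior to surgery), at 90, 180 and 360 days". The list is REC, KTW, GT, PPD, BoP and PI, so it contains neither a VAS nor an aesthetic rating.

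Section 8.3, repeated in the synopsis, says that "the significance of the difference within each group and between groups before and after treatment will be evaluated" by "paired samples t-test or two independent samples t-test, as appropriated", "regarding all numerical data (REC, KTW, GT, PPD, percentage of root coverage and VAS scale". The flow-chart row "Pain assessment (VAS" carries a single mark, which agrees with the "questionnaire about post-operative pain" that section 7.5 places at 7 ± 2 days. Section 4.2 lists percentage of root coverage (RC%) at 3, 6 and 12 months only.

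Section 5.1 has the allocation envelope opened just after anaesthesia, and the synopsis describes the trial as open label.

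**The concern.** How a patient rates the look of the gums after surgery is likely to depend partly on how they rated it before. Without a pre-surgery score, that between-patient variation stays in the error term, and a chance imbalance between two small arms cannot be examined or adjusted for. The result also cannot be expressed as improvement. A pre-surgery rating cannot be recovered once a patient has been operated on, so the choice has to be made before enrolment.

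A lesser matter of wording goes with this. The before-and-after sentence in section 8.3 covers two variables with no usable pre-surgery value, pain VAS and RC%. It also leaves open whether aesthetics falls under the VAS. If it does not, section 8.3 names no analysis for aesthetics.

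**Working it through.** **Inputs**
- From section 8.1: 17 patients per arm before the dropout allowance (18 with it), alpha 0.05, power 80%, SD 10 points, difference of interest 10 points, mean root coverage 85 to 95%.
- Assumed: a two-sided test, since sidedness is not stated.
- Assumed: a correlation r between pre- and post-surgery aesthetic ratings of 0.1, 0.3 or 0.5. The documents give no value.

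**The plan's own figure.** A difference of 10 with SD 10 is 1 SD. The two-sided two-sample t-test needs 16.71 per arm, rounded up to 17, with 80.7% power at 17. The stated 17 is reproduced. It rests on a between-arm comparison of mean root coverage, which needs no pre-surgery RC%.

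**Detectable difference for aesthetics, unadjusted.** With 17 per arm, the same test has 80% power for about 1 × √(16.71/17) = 0.991 SD.

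**With baseline adjustment.** Residual variance is multiplied by (1 − r²), so the detectable difference is 0.991 × √(1 − r²):

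| Assumed r | Variance removed | Detectable difference |
|---|---|---|
| 0.1 | 1% | 0.991 × 0.995 = 0.986 SD |
| 0.3 | 9% | 0.991 × 0.954 = 0.945 SD |
| 0.5 | 25% | 0.991 × 0.866 = 0.858 SD |

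These figures are slightly favourable, because they ignore the cost of estimating the covariate slope. For a normally distributed covariate and n per arm, that cost multiplies the variance by about 1 + 1/(2n − 4) = 1 + 1/30, and so the detectable difference by √(31/30) = 1.017. The three rows become about 1.00, 0.96 and 0.87 SD. Adjustment breaks even where (1 − r²)(31/30) = 1, that is r = √(1/31) = 0.18.

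**The wording of section 8.3 against the schedule**
- REC, KTW, GT and PPD are recorded before and after surgery, so both paired and between-arm tests can be run.
- Pain VAS is recorded once, at about Day 7. Only a between-arm test can be run.
- RC% is listed only after surgery. The documents give no formula. If it is the usual reduction from baseline REC, its starting value is 0 by construction. A paired test with the plan's means, SD and n would give t = 85/(10/√17) = 35.0 to 95/(10/√17) = 39.2, which says nothing about the choice of technique. The between-arm test can be run and is informative.
- Patient-rated aesthetics has no baseline and no named scale. A between-arm test at 6 and 12 months can be run.

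**The case against.** The strongest objection is that nothing here is an error. The objective is a comparison between randomised techniques, which is unbiased without a baseline. No section promises change from baseline in aesthetics, and the 6- and 12-month schedule matches section 4.2. Aesthetics is one of eight secondary bullets, the trial was not sized for it, and the benefit of adjustment turns on an unstated correlation. At r = 0.1 there is in practice no gain. All of this stands. It limits the point to an inexpensive improvement, but it does not remove the case for one question that cannot be asked later.

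A reader might also infer that section 8.3 prescribes a paired test that is impossible for pain VAS and meaningless for RC%. The full sentence does not support that. It covers differences between groups as well as within them, and it offers "paired samples t-test or two independent samples t-test, as appropriated". For Day 7 pain and for RC% the independent-samples test is the suitable option, and the planned data supply it. Moreover, a paired test on REC is almost as predictable as one on RC%, so predictability alone does not make the RC% wording a fault. What remains is loose drafting: the sentence does not assign tests to variables or identify the VAS.

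**Conclusion.** The point holds as a low-cost improvement. Patient-rated aesthetics is a named part of the secondary objective, and the plan collects it only after surgery. The comparison between arms is valid as planned; a reader should not infer that the missing baseline biases it or makes it unusable. What is given up is precision, and the ability to account for patients' starting point.

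At 17 per arm, a two-sided 0.05 test and 80% power, the detectable difference would move from about 0.99 SD to between 0.986 SD (r = 0.1) and 0.86 SD (r = 0.5), before the small cost of fitting the covariate. The gain is modest at r = 0.3 to 0.5 and vanishes below about r = 0.18. The correlations are assumptions.

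The section 8.3 wording needs clarifying but is not an analysis error, and clarifying it would change no between-arm result. The primary outcome (complete root coverage at 12 months, by Fisher's exact test) and the sample size are unaffected.

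**What to change.** 1. Name the scale for patient-rated aesthetics. Add a flow-chart row for it with marks at 6 months, 12 months and one pre-surgery time, at screening or on Day 0 before anaesthesia. Because the envelope is opened after anaesthesia, either time keeps the rating free of knowledge of the allocation.
2. State in section 8.3 that arms are compared on this rating at 6 and 12 months, adjusting for the pre-surgery score.
3. As clarification, in sections 1 and 8.3, limit paired before-and-after tests to REC, KTW, GT and PPD. State that RC% (3, 6 and 12 months) and Day 7 pain VAS are compared between arms only, and say which measure the VAS refers to.

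The cost is one extra question per patient at a visit already scheduled, one covariate in a secondary analysis, and a few lines of text. No extra visit, procedure or staff is needed. Items 1 and 2 must be settled before the first patient is operated on. Item 3 can be made at any time before analysis.

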4.1. Primary outcome

- percentage (%) of complete root coverage (CRC) at 12 months

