5. STUDY DESIGN

5.1. Description of the protocol

The present research is a monocentric prospective parallel randomized controlled clinical trial.

Patients presenting multiple gingival recessions in the maxillae will be enrolled in the study after having signed an informed consent. Recessions will be treated by means of two mucogingival surgery techniques: modified coronally advanced flap (MCAF) and modified coronally advanced tunnel technique (MCAT), in association with the use of a collagen matrix (CM).

An allocation sequence by means of a computer-generated random list will be created and a sealed opaque envelope will contain the type of treatment assigned to each patient. The opaque envelope will be opened immediately after performing anesthesia.

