6.1. Inclusion criteria

Subjects must be males and females of at least 18 years of age with:

- multiple (i.e., at least 2) Miller Class I and/or II gingival recessions located in the maxillae, with an apico-coronal extension (i.e., defect depth > 1 mm with at least one defect > 2 mm) and with at least 1 mm of residual keratinized tissue,
- good general health, with no systemic diseases that could influence the outcome of the therapy,
- healthy periodontal conditions (i.e., no presence of sites ≥ 4 mm and/or presence of intra-bony defects in the selected sites),
- adequate oral hygiene (full mouth plaque score (FMPS) of <25% at baseline (following initial oral hygiene instructions and prophylaxis),
- an adequate control of inflammation (full mouth bleeding score [FMBS]) of <25% at baseline (following initial oral hygiene instructions and prophylaxis).

Subjects must have voluntarily signed the informed consent before any study related action and must be committed to the study and the required follow-up visits.

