8. STATISTICAL CONSIDERATIONS

8.1. Sample size calculation

The range of mean root coverage percentage of the two mucogingival techniques which can be found in literature varies between 85% and 95%. While the value of variability (SD) obtained in previous articles is 10%. On the basis of these settings, the sample dimension has been calculated using $\alpha = 0.05$ and the power (1- β) of 80%. The minimal significant value considered is 10%.

So, the needed number of patients to be enrolled in this study is 17 for the test group MCAF + Fibro-Gide and 17 for the MCAT + Fibro-Gide. However, the number of patients will be increased of 1 patient for each arm considering the possibility of dropout, so the required number will be 18 for each group.

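### Cheap improvement, not an error: the primary test of complete root coverage makes no use of baseline recession depth, which is already collected

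*Combined protocol and SAP*

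**What the plan says.** Section 4.1 sets the primary outcome as "percentage (%) of complete root coverage (CRC) at 12 months", and the null hypothesis in 8.2 concerns the same outcome. For its between-arm comparison, section 8.3 states "Fisher's exact test will be applied for categorical data (frequency of complete root coverage". The synopsis gives the same test in its statement of the primary method. The significance rule is "Differences will be considered statistically significant when the p-value was <0.05". Section 8.3 also says that p-values will come from permutation methods.

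Baseline depth is collected. The synopsis says "The following measurements will be recorded at baseline (prior to surgery), at 90, 180 and 360 days: Gingival recession depth (REC in mm", and the flow-chart marks REC at screening. Eligibility in 6.1 sets only lower limits on depth: "defect depth > 1 mm with at least one defect > 2 mm".

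Nothing in the plan ties baseline depth to the CRC comparison. On allocation, 5.1 says "An allocation sequence by means of a computer-generated random list will be created", and no stratification is described. Section 8.3 does plan a model: "A mixed model will be built to take into account the variability due to patient and tooth factors differentially". It names no outcome, fixed effect or covariate for that model, and the synopsis statement of the primary method leaves the model out.

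**The concern.** CRC is 12-month recession depth cut at zero. Depth at entry is therefore the baseline value of the variable being dichotomised, and a deeper defect needs more gain to count as a success. If depth predicts CRC, a test that ignores it leaves explainable variation in the comparison and loses some power. With 17 or 18 patients per arm, mean depth can also differ between arms by chance, and the plan has no stated way to allow for that in the estimate. Choosing to adjust only after an imbalance has been seen would be open to dispute. Pre-specifying the adjustment avoids this.

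**Working it through.** **The plan's own figure.** Section 8.1 uses a difference of 10, SD 10, alpha 0.05 and power 80%. The normal approximation gives n = 2 × (1.96 + 0.84)² × (10/10)² = 15.7, so 16 per arm. The exact t-test calculation gives power 78.1% at 16 and 80.7% at 17. The stated 17 per arm reproduces, two-sided. It is sized on mean root coverage percentage, which is not the primary outcome. It supplies no CRC rate and says nothing about how depth relates to CRC.

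**Power for CRC.** The inputs are assumptions:
- 17 per arm, one CRC value per patient, two-sided alpha 0.05.
- Standard normal baseline depth, and CRC from a probit latent variable with correlation ρ to depth.
- The adjusted test fits CRC on depth by logistic regression without arm, sums the residuals by arm, and permutes arm across patients (999 permutations, 8,000 trials per setting, Monte Carlo standard error about 0.5 points or less).

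The comparator is the same test with an uninformative covariate (ρ = 0), so that the coarseness of Fisher's test is not counted as a gain from depth.

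| True CRC | ρ = 0 | ρ = 0.3 | ρ = 0.5 | Gain at 0.3 | Gain at 0.5 |
|---|---|---|---|---|---|
| 45% vs 90% | 82.4% | 84.6% | 88.0% | 2.2 | 5.6 |
| 50% vs 90% | 74.2% | 76.6% | 80.7% | 2.4 | 6.5 |
| 40% vs 85% | 78.6% | 80.8% | 85.6% | 2.2 | 7.0 |
| 85% vs 95% | 12.7% | 13.2% | 14.0% | 0.5 | 1.3 |
| 60% vs 70% | 8.6% | 8.9% | 9.7% | 0.3 | 1.1 |
| 60% vs 60% (size) | 5.2% | 4.8% | 4.8% | – | – |

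Allowing for simulation error, the gain for CRC differences of 40 to 45 points is about 1 to 3 points at ρ = 0.3 and about 6 to 8 at ρ = 0.5. For a 10-point difference it is about 1 point, and power stays very low either way.

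**Second model as a check.** At 18 per arm and CRC 40% vs 80%, Fisher's exact power is 61%. The adjusted permutation test with an uninformative covariate has 68%, so about 7 points come from removing discreteness and not from depth. If the log-odds of CRC fall by 0.5, 1.0, 1.5 or 2.0 per SD of depth, power is about 72%, 76%, 82% or 87%. The gain from depth itself is then 72 − 68 = 4 points up to 87 − 68 = 19. The upper figure needs an odds ratio of e² = 7.4 per SD, a strong assumption.

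**Chance imbalance.** The standardised difference in mean depth has standard deviation √(2/17) = 0.343. P(|difference| > 0.5 SD) = 2 × [1 − Φ(0.5/0.343)] = 14.5%. At 18 per arm the standard deviation is 0.333 and the probability 13.4%.

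**What such an imbalance does.** Take CRC at 60% in both arms. The normal density at the 60% point is 0.386, so a 0.5 SD imbalance shifts the expected CRC difference by about 0.5 × ρ × 0.386:
- ρ = 0.3: 0.058, about 6 points.
- ρ = 0.5: 0.097, about 10 points.

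The standard error of the CRC difference is √(2 × 0.6 × 0.4/17) = 0.168, about 17 points. The shift is about a third to three-fifths of one standard error.

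**The case against.** A reader might infer that Fisher's test is biased here, or that it mistakes a depth imbalance for an effect of technique. The documents do not support that. Treatment is randomised, and the null distribution of the test already allows for chance imbalance in every baseline variable. Type I error is not inflated; for Fisher's test at 60% vs 60% it is in fact about 2.4 to 2.9%. Adjustment is an efficiency choice, and this objection stands in full.

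A reader might also infer that adjustment would repair the power of the primary comparison. It would not. The useful gains need true CRC differences of 40 to 45 points, whereas the only difference in the plan is 10 points, stated for mean coverage. The sizing of the trial on a different outcome is a separate and larger matter.

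Third, the planned mixed model could already cover this. Section 8.3 promises patient-level and tooth-level analysis of each parameter, 8.2 treats CRC as a clinical parameter, and tooth depth could be one of the tooth factors. That reading is possible, so it would be too strong to say that the plan excludes adjustment. As written, though, the model names no covariate and is not the stated primary method, so the gap is in specification.

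Finally, the strength of the depth-CRC association and the spread of depth at entry are not in the documents. This stands, and it is why the gain can only be given as a range.

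**Conclusion.** The point holds as a low-cost improvement. The only between-arm test named for the primary outcome ignores a baseline measurement that is collected on every patient and is closely tied to what counts as success. The expected benefit is modest: about 1 to 3 points of power at a latent correlation of 0.3 and 6 to 8 at 0.5. Those figures assume 17 per arm, CRC differences of 40 to 45 points and one CRC value per patient. A stronger association would give more; no association, or a true difference near 10 points, would give almost nothing. About 14% of trials of this size would show a depth imbalance above 0.5 SD, which would move the observed CRC difference by roughly 6 to 10 points against a standard error of about 17. Pre-specified adjustment would take most of that out of the estimate. The validity of the planned test is not in question.

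**What to change.** In section 8.3 and the synopsis, first state the unit of the primary CRC analysis. Each patient has at least two recessions, and section 4.1 does not say whether CRC is counted by tooth or by patient. Then pre-specify one baseline depth covariate that matches that unit.

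- **One CRC value per patient:** use a patient-level summary of baseline REC fixed in advance. Use the mean, or the deepest defect if CRC means that all treated teeth are covered. Obtain the p-value by permuting arm across patients, which 8.3 already plans.
- **CRC by tooth:** put arm and the tooth's baseline REC in the planned mixed model as fixed effects, with a patient random effect.

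In either case, report an adjusted CRC difference with a confidence interval, because a permutation test on residuals gives neither by itself. Keep the unadjusted frequencies and Fisher's test, on one value per patient, as supportive. With 36 patients, one covariate is enough.

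The cost is a few lines of text and a short script in the software already named; no new data, visits or patients are needed. The downside is a primary test less familiar than a 2×2 table, with little return if depth proves weakly prognostic.

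### Fisher's exact test for patient-level CRC is valid but runs well below 5%; Boschloo's exact test gains about 0 to 13 points of power at no cost in patients

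*Combined protocol and SAP*

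**What the plan says.** Section 4.1 names a single primary outcome, "percentage (%) of complete root coverage (CRC) at 12 months", and section 8.2 frames the null hypothesis on CRC. For its frequency, section 8.3 says that Fisher's "exact test will be applied for categorical data (frequency of complete root coverage"); the synopsis says the same. Section 8.3 adds: "P-values will be computed by means of permutation methods to avoid any distributional assumptions or asymptotical approximation". The significance rule is "Differences will be considered statistically significant when the p-value was <0.05", with no statement of one- or two-sided testing.

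Section 8.3 announces both patient-level and tooth-level analyses and a mixed model, but does not say at which level the Fisher test is applied or which level is primary. Section 6.1 requires at least two recessions per patient.

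Section 8.1 arrives at 17 patients per arm, raised to 18 for dropout. Its inputs concern mean root coverage: a literature range of 85% to 95%, an SD of 10%, alpha 0.05, "and the power (1- β) of 80"%, and "The minimal significant value considered is 10"%. No CRC rate, CRC difference or power for the CRC comparison is given anywhere.

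**The concern.** Fisher's test conditions on the total number of successes. In small arms few tables are then possible, so the attainable p-values are coarse and the true type I error sits well under the nominal 5%. In a trial of 36 patients, unused alpha on the primary comparison is power given up.

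The plan's permutation p-values might look like a remedy. With one binary outcome per patient they are not, because shuffling arm labels with the number of successes fixed generates the same hypergeometric distribution that Fisher uses.

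What is at stake is a borderline primary result. With 18 per arm, 9/18 v 15/18 gives Fisher p = 0.075 and 10/18 v 16/18 gives p = 0.060. Both miss 0.05 under Fisher, and both are significant under Boschloo's test with type I error still held at or below 5%.

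**Working it through.** **1. Reproduce the plan's figure (section 8.1).** Inputs: difference 10, SD 10, alpha 0.05, power 80%. Normal approximation: n = 2 × (1.96 + 0.842)² × (10/10)² = 15.7, so 16 per arm. The exact noncentral t calculation gives power 0.781 at 16 and 0.807 at 17, so 17 per arm. The stated figure is reproduced as a two-sided t-test on mean root coverage; a one-sided calculation gives 13 and does not fit. I therefore take alpha as two-sided throughout.

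**2. True size of the two exact tests.** Assume one binary CRC outcome per patient and n per arm. For a rejection region R, the type I error at common rate p is the sum over all (x, y) in R of b(x; n, p) × b(y; n, p), where b is the binomial probability. Size is the maximum over p, on a grid from 0.001 to 0.999. All (n+1)² tables were enumerated.

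- Fisher rejects when its two-sided p < 0.05.
- Boschloo uses Fisher's p-value as the ordering statistic, with the largest cut-off that keeps the size at or below 0.05: 0.080 at n = 17 and 0.088 at n = 18.

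| n per arm | Fisher, maximum size | Fisher at CRC rate 70% | Fisher at 90% | Boschloo, maximum size |
|---|---|---|---|---|
| 17 | 2.4% | 2.0% | 0.8% | 4.3% |
| 18 | 2.9% | 2.2% | 0.9% | 4.8% |

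Both Boschloo cut-offs exceed 0.05, so its rejection region contains Fisher's. It therefore cannot have lower power at any pair of rates.

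**3. Power.** Power is the sum over R of b(x; n, p1) × b(y; n, p2). Every CRC rate below is an assumption, because the documents give none. Gains are taken from unrounded powers.

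| n per arm | Assumed CRC rates | Fisher | Boschloo | Gain (points) |
|---|---|---|---|---|
| 17 | 85% v 95% | 4.4% | 4.5% | about 0 |
| 17 | 75% v 95% | 22.0% | 22.5% | 0.5 |
| 17 | 60% v 90% | 39.2% | 45.7% | 6.5 |
| 17 | 40% v 80% | 56.1% | 66.3% | 10.2 |
| 18 | 85% v 95% | 5.3% | 6.4% | 1.2 |
| 18 | 30% v 70% | 60.9% | 64.6% | 3.7 |
| 18 | 50% v 90% | 66.8% | 78.0% | 11.1 |
| 18 | 60% v 90% | 42.6% | 55.1% | 12.6 |

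Over a 5-point grid of rate pairs where Fisher's power is 50% to 85%, the median gain is 7.3 points (range 3.0 to 11.3) at n = 17 and 8.2 points (2.2 to 12.6) at n = 18. For a 10-point CRC difference it is 0 to 3.6 points at n = 17 and 1.2 to 4.4 at n = 18.

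**4. If teeth are the unit.** A beta-binomial simulation (20,000 replicates, 17 patients per arm, CRC 70% in both arms) applied Fisher to teeth as if they were independent. With assumed intraclass correlations of 0.2 and 0.4, type I error was 4.3% and 6.1% with two teeth per patient, and 6.9% and 10.9% with three. Conservatism can turn into excess error, and an unconditional test on teeth would not cure that.

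**The case against.** Fisher's exact test is a standard choice at this size and controls type I error. A reader might infer that section 8.3 contains a mistake. It does not: choosing between conditional and unconditional exact tests is a choice between valid methods. That objection stands and sets the weight of the point.

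A reader might also attach a fixed figure to the loss, such as 8 to 10 points of power. The documents do not support one. Such a figure comes from assuming differences of roughly 40 points between two techniques that use the same matrix. Nor is a negligible gain confined to cases where both rates are 85% or more: at 17 per arm, 75% v 95% gains 0.5 points and 65% v 95% gains 2.1.

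A third tempting inference is that Fisher erodes the stated 80% power, or that Boschloo would restore it. That 80% belongs to a 10-point difference in mean root coverage, and no power was ever stated for CRC. Sizing on a different endpoint from the primary one is a separate and larger problem. If CRC rates were 85% v 95%, the usual two-proportion formula needs (1.96 × √(2 × 0.90 × 0.10) + 0.842 × √(0.85 × 0.15 + 0.95 × 0.05))² / 0.10², about 140.1, so 141 per arm. Boschloo reaches 6.4% there with 18 per arm.

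Finally, the unit of analysis is open. If CRC is analysed by tooth, the sizes in the working do not apply. If it is analysed as each patient's percentage of covered teeth, a permutation test over patients is not the same as Fisher. This also stands, and it makes the point conditional on a patient-level binary outcome.

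**Conclusion.** The point holds as a conditional efficiency improvement. For one binary CRC outcome per patient, two-sided testing at 0.05 and 17 or 18 patients per arm, Fisher uses at most 2.4% or 2.9% of the 5% allowed. Boschloo uses at most 4.3% or 4.8%, so it stays within the limit and is never less powerful.

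The size of the gain is about 0 to 13 points, depending on unknown CRC rates and on whether 17 or 18 patients per arm are analysed. It is near the middle or top of that range for many differences of 30 to 40 points, and small for differences near 10 points. The change does not make the trial adequately powered for CRC, and it should not be presented as doing so.

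**What to change.** Before data are seen, amend section 8.3 and the synopsis to:

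- define the primary CRC outcome as one binary outcome per patient, stating how a patient's several recessions combine into it;
- test it with Boschloo's unconditional exact test at two-sided 0.05, with the cut-off computed for the numbers actually analysed in each arm;
- report the risk difference with an exact unconditional 95% CI;
- keep tooth-level CRC in the mixed model, because neither Fisher nor Boschloo is valid on clustered teeth.

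The cost is a few lines of text. It needs no extra patients or visits, type I error stays at or below 5%, and R, which section 8.3 already names, can run the test. The mismatch between the sample size calculation and the primary endpoint needs its own correction.
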